**See the help text for additional guidance**

**1. A statement explaining the study design**

**Study Design:**

The proposed study consists of two parts.

Part 1 involves formative research through a focus group to gather insights and reach saturation.

Part 2 is a single-arm pre and post-test trial with the objective of evaluating the efficacy of an educational interventional program.

The study aims to increase cervical cancer screening (CC-S) and HPV vaccine (HPV-Vax) rates among Muslim American women (MAW) in Virginia, leading to a reduction in cervical cancer (CC) incidence and mortality.

2. A detailed description of all the procedures that will be followed to carry out the study, preferably in sequential order, and in sufficient detail that the study's methods could be replicated.
  - a. Part 1 - Formative Research: Conduct a focus group with 10 participants until saturation is reached.
  - b. Part 2 - Single-arm Pre and Post-test Trial: Enroll 20 participants to evaluate the educational program's effectiveness.

Participants will complete a baseline survey to assess their knowledge, attitudes, CC-S and HPV-Vax practices, and predisposing factors.

The survey will cover topics such as CC knowledge, experiences of medical mistrust, discrimination, spiritual coping, and fatalism.

3. The schedule and frequency of when and how procedures will be conducted (e.g. in person, online, phone, paper, etc.)

All procedures will be conducted in person at the Islamic Centers, except for follow-up phone calls.

Recruitment will occur during regular Friday prayers and religious holidays.

Participants will receive a brochure explaining the study and be screened for eligibility by the Research Assistant (RA). Eligible participants will be given a telephone contact for enrollment at a more convenient time.

The consent process will involve verbal explanation, providing the consent form in English, and allowing participants to ask questions. Follow-up surveys and confirmations will be conducted via phone calls.

4. A description of all research measures/tests/interventions that will be used, including analyses/tests conducted on specimens/biological samples (if applicable)

**Power Analysis:** No power analysis for this study. A target sample size of 20 participants has been determined based on PhD committee, the purpose of the project is training for the STUDENT.

Measures: Validated scales and surveys will be used to measure

Age: Age can be measured using a simple demographic question such as "What is your age?" in the pre- and post-intervention surveys.

Education: Education level can be measured using a simple demographic question such as "What is the highest level of education you have completed?" in the pre- and post-intervention surveys.

Modesty and Conservatism: can be measured using a combination of demographic questions and attitudinal scales.

For example, demographic questions could include "How important is modesty in your culture?" or "How conservative would you describe yourself?" while attitudinal scales could include items such as "I am comfortable discussing reproductive health issues with my healthcare provider" or "I am willing to discuss cervical cancer prevention activities with my family and friends."

Cervical Screening and HPV Vaccine Uptake: can be measured using self-reported questions such as "Have you ever had a Pap smear?" or "Have you ever received the HPV vaccine?" in the pre- and post-intervention surveys. Additional questions can also be included to determine the frequency and timing of screening and vaccine uptake.

Participants' Knowledge and Attitude: can be measured using a combination of open-ended and closed-ended questions.

Open-ended questions could include "What do you know about cervical cancer prevention activities?" while closed-ended questions could include "Do you believe that cervical cancer screening is important?" or "Do you believe that the HPV vaccine is safe and effective?"

Feasibility of Intervention: can be measured by tracking enrollment rates, attendance rates, and completion rates in the pre- and post-intervention surveys.

Additional questions can also be included to assess the overall acceptability of the intervention among participants.

Self-efficacy: can be measured using a self-efficacy scale specific to cervical cancer screening, such as the Cervical Cancer Screening Self-Efficacy Scale (CCSES), as described in the previous answer.

Acceptability of the Program: can be measured using a satisfaction survey at the end of the intervention program. The survey could include questions such as "Did you find the program useful?" or "Would you recommend this program to a friend?"

Outcomes:

The primary outcome in increase the number of women who undergo cervical cancer screening. Secondary outcomes include an increase in knowledge and awareness, an increase in self-efficacy, and improvement in attitudes towards cervical cancer prevention.

Long-term outcomes include a reduction in cervical cancer incidence and mortality, sustainability of behavior change, and a reduction in healthcare costs associated with advanced-stage cancer treatment.

Moderator factors that can influence the effectiveness of the program include age, education level, ethnicity, socioeconomic status, Mediating mechanisms that explain how the program leads to its outcomes include improved knowledge and awareness, increased self-efficacy, attitude change, increased and social support,

Identifying and addressing moderator factors and mediating mechanisms can help to tailor the program to the specific needs and preferences of the target population and maximize its effectiveness

**Key Study Variables:** Socio-demographic variables, cultural/religious practices, cancer literacy, knowledge, perceived risk, barriers, benefits, and participation in preventive measures.

**Evaluation Measures:** Intervention acceptance will be self-reported, covering challenges, barriers, facilitators, likes/dislikes, and suggestions for improvement.

This study aims to address barriers to CC prevention among MAW through an educational intervention, using a sequential approach of formative research and a single-arm trial. The study will be conducted at Islamic Centers, involving in-person procedures, phone follow-ups, and self-report measures. The proposed methods are designed to evaluate the effectiveness of the educational program and its impact on CC-S and HPV-Vax rates in the target population.

**Statistical Tests:** Statistical tests such as t-tests or ANOVA can be used to analyze the data from the pre-post survey. These tests will help determine whether there are statistically significant differences between the pre- and post-survey results and whether the intervention had a significant effect on participants' knowledge and acceptance of cervical cancer prevention.

**7. \* The IRB only reviews research activities, so indicate for each of the study activities described in the question above or in the protocol which activities are:**

- Being performed exclusively for research purposes (i.e. they would not otherwise be done apart from this study) **VERSUS**.
- Alterations of routine activities/procedures (e.g. the study is altering the timing, frequency, method, location, amount, etc.) **VERSUS**.
- Being done for other purposes and whose data/results will be used secondarily in the study (e.g. standard medical or psychological tests, routine education practices, quality improvement initiatives, etc.).

See the help text for additional guidance

The study is being performed exclusively for research purposes.

**8. If applicable, describe alternatives (research or non-research) that are available to potential participants if they choose not to participate in this study:**

**9. Upload any supporting tables or documents (e.g. protocol documents, figures/tables, data collection forms, study communications/reminders):**

Upload ALL instruments/guides that will be used or that participants will experience (i.e. see, hear, complete), including measures, scripts/questions to guide interviews, surveys, questionnaires, observational guides, etc.:

Upload ALL recruitment and screening materials, including such as ads, flyers, telephone or in-person scripts, letters, email invitations, TelegRAM announcements, and postcard reminders, screening scripts, screening forms, and screening measures:

Document Name	Document	Version	Date Modified By	Uploaded Type	Approved
View Consent form focus group	[name]- Consent 0.03 from of focus	7/8/2023 1:09 AM	[name]	Consent/Assent/Information Sheet	

Document Name	Document	Document	Version	Date Modified By	Uploaded Type	Approved
group 05.12.2023.pdf						
View Consent form - Intervention program	[name]- Consent 0.04 from of Intervention group 05.12.2023 copy.pdf		7/8/2023 1:09 AM	[name]	Consent/Assent/Information Sheet	Yes
View Fund Plan	[name] -Budget 04.13.2023.xlsx	0.03	5/12/2023 11:52 AM	[name]	Funding Proposal	Not Applicable
View Education session	[name] Education session guide , intervention intervention group- 04.07.2023.docx	0.02	5/12/2023 10:52 AM	[name]	Other	Yes
View Timeline Plan	[name] timeline for PROMIS women Project.docx	0.02	5/12/2023 10:43 AM	[name]	Other	Yes
View Conceptual model	[name] Conceptual Model 05.12.2023.docx	0.02	5/12/2023 10:40 AM	[name]	Research Measure	Yes
View Flayer 2	[name] Flyer Version 05.12.2023.docx	0.01	5/12/2023 10:39 AM	[name]	Other	Yes
View [name]-Focus group script guide	[name] -Focus Group Script Guide.docx	0.02	5/12/2023 10:24 AM	[name]	Other	Yes
View Participants -RA communication script	Participants -RA communication script .docx	0.01	5/12/2023 6:45 AM	[name]	Other	Yes
View Study Survey( Pre-post and satisfactory scales)	Survey- Promise women project 05.12.2023.docx	0.01	5/12/2023 6:35 AM	[name]	Research Measure	Yes
View consent form- focus group	Consent from - Focus group 02.20.2023.docx	0.01	2/20/2023 4:32 PM	[name]	Consent/Assent/Information Sheet	No

Document Name	Document	Version	Date Modified By	Uploaded Type	Approved
---------------	----------	---------	------------------	---------------	----------

View VS biosketch	[name] Biosketch for AN 11.14.2022.pdf	0.01	2/20/2023 4:00 PM	[name]	CV/Biosketch	Not Applicable
View Communication log	Communication log.docx	0.01	2/20/2023 3:59 PM	[name]	Other	Yes
View PRMC approval	2022-10-10_MCC-22-19873_PRMC Approval Letter.pdf	0.01	10/10/2022 12:30 PM	[name]	Ancillary Committee Approval	Not Applicable
View Flyer	Flyer 004.08.2022.png	0.01	4/8/2022 6:09 PM	[name]	Other	Yes
View [name] Resume	[name] 06.07.2021.pdf	0.01	4/3/2022 3:47 PM	[name]	CV/Biosketch	Not Applicable

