**See the help text for additional guidance.**

The principal investigator (PI) has a community partnership with the Islamic Center of Richmond, where the research team will distribute flyers about the project (see attachment). The research team will be present at the Mosque at predetermined times where women could approach study team members to ask questions, sign up for participation, and schedule appointments.

1) Identification of potentially eligible participants:

- The research team will distribute flyers about the project at the Islamic Center of Richmond to identify potentially eligible participants.
- The education material will be mentioned as PDF in the docs section

2) Recruitment procedures to invite participation in the study:

Place: The research team will be present at the Mosque during predetermined times.

Participants: Women interested in participating can approach study team members to ask questions, sign up for participation, and schedule appointments.

Written recruitment materials, such as flyers, will be distributed to provide information about the study.

Verbal recruitment materials will be used when study team members interact with potential participants.

The research assistant will handle contact with potential participants, including scheduling interviews and baseline surveys.

Recruitment procedures will take place at the Islamic Center of Richmond.

3) Eligibility screening prior to consent and how those activities will be carried out:

During these interactions, eligibility screening will be conducted to ensure participants meet the study criteria.

The research team will use a standardized screening tool or questionnaire to assess eligibility.

For focus group meetings, participants will be screened for eligibility before being scheduled for interviews.

For the one-arm clinical trial, participants will be screened for eligibility during the scheduling of baseline surveys.

The education materials will be clearly outlined in the study plan PDF.

The survey will be given to the potential participants in person ( hard) or through QR code through redcap.

Summary the intervention :

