The intervention group will consist of 20 participants who will receive one education session divided into three sections/videos. The session will be offered in a single day and last 1.5 hours. The session will include the following topics: 1) Risk of HPV infection (30 minutes), 2) Cervical cancer risk (30 minutes), and 3) Advantages and benefits of early screening and the HPV vaccine (30 minutes).

All participants from both groups will be given the survey at month 0 (baseline) after the delivery of the educational material. The survey will be self-report, available in both hard copy and electronic form with a QR code for Redcap.

Participants are expected to take approximately 45 minutes to complete the survey.

The Islamic center offer private room to practice the research activities in both phases ( Focus group and single arm trial)

**5. \* Does this study have a separate protocol document (i.e. a multisite or sponsor's protocol) that contains a detailed description of the study's methodology?**

Yes

No

**6. \* Since a separate protocol document is not uploaded, describe the proposed research using language understandable to those IRB committee members whose expertise is not scientific. The description must include:**

- 1. A statement explaining the study design**
- 2. A detailed description of all the procedures that will be followed to carry out the study, preferably in sequential order, and in sufficient detail that the study's methods could be replicated**
- 3. The schedule and frequency of when and how procedures will be conducted (e.g. in person, online, phone, paper, etc.)**
- 4. A description of all research measures/tests/interventions that will be used, including analyses/tests conducted on specimens/biological samples (if applicable)**

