## PROMIS WOMAN Education Program : ImProving ceRvical cancer preventOn methods among Muslim Americans WOMEN

### Active Internet Data Collection

**1. \* Describe the platform/technology chosen for collecting the data and transmitting data securely over the Internet. If proposing a non-VCU approved platform, give the rationale for selecting the technology instead of a VCU-approved platform.**

The chosen platform for collecting survey data in this study is REDCap (Research Electronic Data Capture). REDCap is a widely used, secure, and HIPAA-compliant web-based application specifically designed for research data collection and management. It provides a user-friendly interface for designing surveys, capturing data, and generating reports.

For note recording, the Apple system will be utilized, likely referring to Apple devices such as iPads or iPhones. These devices offer built-in voice recording features that can be used by the research assistant during interviews or other data collection activities.

The rationale for selecting REDCap as the survey collection platform is its established reputation as a secure and reliable tool for research data. It is designed to meet rigorous data protection standards, ensuring the privacy and confidentiality of participants' information. Additionally, REDCap offers a range of features for data validation, quality control, and export options, which contribute to efficient and accurate data management.

While using a VCU-approved platform is typically encouraged to maintain consistency and alignment with institutional policies, the decision to utilize REDCap and the Apple system may stem from specific functionalities and familiarity with these technologies. Researchers may have found that these platforms meet their data collection and recording needs effectively, and they have confidence in their security and reliability.

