**2. \* Describe how each of the risks/harms/discomforts identified above will be minimized:**

**Psychological Risks:** To minimize psychological risks and address emotional discomfort, several measures will be implemented. Participants will have the option to take breaks during the study if needed, ensuring their well-being and allowing them to manage any emotional distress that may arise. Additionally, participants will be provided with resources and information about counseling services, should they require additional support. The research team is committed to ensuring that participants' mental health and emotional well-being are prioritized throughout the study.

**Research Data Risks:** To mitigate research data risks and ensure participant privacy, robust measures will be implemented. De-identification and coding processes will be employed to remove any identifying information from the data, ensuring confidentiality. The interview answers will be recorded using an electronic data capture system hosted on secure VCU servers accessible only to authorized researchers. These servers comply with stringent security protocols and maintain researcher-only access, further safeguarding the confidentiality of participant data.

**Social or Legal Risks:** To address social or legal risks, several strategies will be employed to ensure cultural sensitivity and community engagement. Expert researchers will review the educational sessions to ensure their appropriateness and alignment with cultural norms. Community leaders from the target population will provide input and review religious materials included in the sessions, ensuring cultural accuracy and relevance. The research assistant involved in the study is a member of the same community and has prior experience conducting studies in Islamic centers, establishing trust and rapport. The research team will consist of female members only, including the peer researcher and primary researcher, creating a safe and comfortable environment for participants. The education sessions will be conducted in a private setting within the mosque, respecting the cultural and religious values of the participants and maintaining privacy.

**3. \* Describe any potential risks or harms to a community or a specific population based on study findings (e.g. information that could be stigmatizing or derogatory):**

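### The plan conflicts on when and how the post-test is given; if it is given by phone, the pre-post change behind H1 is confounded with a change of survey mode

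*Combined protocol and SAP*

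**What the plan says.** Part 2 is an uncontrolled before-and-after study of 20 women (Study Procedures, item 6). H1, that knowledge and acceptance improve, rests on comparing pre-test with post-test answers by t-test or ANOVA.

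On mode, the schedule in item 6 says: "All procedures will be conducted in person at the Islamic Centers, except for follow-up phone calls". It ends: "Follow-up surveys and confirmations will be conducted via phone calls". The design summary later in item 6 describes the study as "involving in-person procedures, phone follow-ups, and self-report measures". Item 4 of the same section differs: "The survey will be given to the potential participants in person ( hard) or through QR code through redcap". Its intervention summary adds: "The survey will be self-report, available in both hard copy and electronic form with a QR code for Redcap". Active Internet Data Collection, item 1, names REDCap as the survey platform and does not separate pre-test from post-test.

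On timing, the intervention summary says that participants "will be given the survey at month 0 (baseline) after the delivery of the educational material". Behavioral Intervention/Task Details, item 1, sets a three-hour event with 90 minutes of education, one 45-minute self-report survey, and a break with lunch. It does not say whether that survey is the pre-test or the post-test. Compensation, item 1, pays for two surveys, one before and one after.

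No section defines the follow-up survey, dates it, or says whether staff read the questions out or only call to prompt completion. The analysis text does not mention mode.

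**The concern.** H1 has nothing behind it except the difference between two surveys in the same women. If the first is self-completed and the second is taken by phone, the change of mode falls exactly on the change from before to after. There is no control arm in which the mode effect could be seen on its own, and if every woman switches mode there is no variation in mode at either time point. A mode term in the model could then not separate the two effects.

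The items cover modesty, attitudes to screening and acceptability of HPV vaccination, where the way a question is put could plausibly change the answer. A shift caused only by mode would be read as a programme effect if it were favourable, or could hide one if it were not. Once the data are collected this way, the analysis cannot undo it.

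**Working it through.** **1. Is the follow-up survey the post-test?** Evidence that it is:

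- The aims list three surveys: pre-test, post-test and satisfaction. The measures text in item 6 puts the satisfaction survey at the end of the programme. That leaves the post-test as the natural follow-up to the baseline survey named in item 6.
- Item 6 makes the number of women screened the primary outcome there, measured by self-report before and after the intervention. A post-test on the day of the session could not show new screening.
- Time at the event: with one survey, 180 − 90 − 45 = 45 minutes remain for the break and lunch. With both, 180 − 90 − 2 × 45 = 0 minutes remain. The event as described holds one survey, so the other falls at another time or place. That leaves room for a phone survey but does not prove one.

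Evidence that it is not, or that the matter is open:

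- The one sentence that places the self-report survey relative to the education puts it afterwards, while calling it baseline. If that survey is the post-test, items 4 and 6 disagree on its mode.
- REDCap is named for survey data generally.
- The phone sentence closes the paragraph on consent and couples surveys with confirmations.

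**2. What would a mode shift do to the test?** The plan has no figure to reproduce: item 6 states that there is no power analysis, and no significance level is given. The inputs are therefore:

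- n = 20 (item 6), and n = 0.80 × 20 = 16 at the boundary of the retention target of more than 80% (H3).
- Assumed: a two-sided 5% level and a paired t-test.
- Assumed: no programme effect, and a mode shift of d standard deviations of the change score. The documents give no value for d, so a range is shown.

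Under these assumptions the test statistic is non-central t with n − 1 degrees of freedom and non-centrality d√n, and

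P(significant) = P(T > t0.975, n−1) + P(T < −t0.975, n−1).

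For n = 20, d = 0.3, the non-centrality is 0.3 × √20 = 1.34 and the probability is 0.247. For n = 16, d = 0.3, it is 0.3 × 4 = 1.2 and the probability is 0.203. In full:

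| d (SD of change) | n = 20 | n = 16 |
|---|---|---|
| 0 | 5.0% | 5.0% |
| 0.1 | 7.1% | 6.6% |
| 0.2 | 13.6% | 11.6% |
| 0.3 | 24.7% | 20.3% |
| 0.5 | 56.5% | 46.5% |

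The two-sided rate is the same whichever way the shift runs. Using one mode at both times sets d = 0 for this source and returns the rate to 5.0%.

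**The case against.** The strongest reply is that no mode switch has been shown. Item 4 describes a self-completed survey after the education, and the research assistant schedules baseline surveys, which suggests separate appointments. A self-completed baseline by appointment and a self-completed post-test at the event would involve no switch. The phone contact could be the satisfaction survey, a later contact or a prompt to complete the form. The timeline, the survey and the communication script are listed as uploads but not reproduced, and may settle the point.

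This stands in part. It rules out treating the switch as fact, but it does not remove the conflict. The benign reading has its own difficulty, since consent for the intervention group is taken at the education sessions. It also leaves item 6 stating in plain words that follow-up surveys are by phone.

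A reader might also infer that women would answer aloud to someone they know and so give more approving answers, because "The research assistant involved in the study is a member of the same community". The documents do not support this. They give the assistant contact with potential participants and scheduling. They do not say who makes the follow-up calls or that questions are read out. Nor do they describe the self-completed survey as private, or show which way a mode effect would run. The confounding does not depend on its direction.

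It is also fair to say that the rejection rates only show that a shifted mean is rejected more often. They are not estimates of bias in this study.

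**Conclusion.** The plan conflicts on when and how the post-test is given, and nothing in it holds the mode constant or deals with mode in the analysis. That much is certain. The further conclusion is conditional: if the phone follow-up survey is the post-test, the H1 contrast is confounded with survey mode, and a single-arm t-test cannot separate the two.

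The size is unknown. For assumed shifts of 0.2 to 0.5 SD and an assumed two-sided 5% level, a programme with no effect would appear significant between 13.6% and 56.5% of the time with 20 women, or between 11.6% and 46.5% with 16. The point should be settled before the first survey is taken, because it cannot be repaired later.

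**What to change.** Reconcile Study Procedures items 4 and 6, Behavioral Intervention/Task Details item 1 and Active Internet Data Collection item 1 so that they agree on the following:

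- The pre-test is completed before the education and the post-test after it, each with a stated time point. This includes correcting the item 4 sentence that puts a baseline survey after the education.
- Both are self-completed, and each woman uses the same mode (paper or REDCap) both times.
- Phone calls are limited to scheduling, reminders and resending the link.
- If a survey has to be taken by phone, the mode is recorded and the analysis is repeated without those women.

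The cost is mainly wording, since paper and REDCap versions are already planned. The event timetable must show where each 45-minute survey is done, because two do not fit with a break in three hours. Follow-up response may be slightly lower, which reminder calls should offset. Other biases of an uncontrolled pre-post comparison remain.
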